6.4.2 OLAPARIB

General Concomitant Medication and Supportive Care Guidelines

There is a potential for interaction of olaparib with other concomitantly administered drugs, but only concomitant medications related to AE or SAE treatment, and other medical conditions deemed necessary by the PI will be recorded on the case report form (CRF). The Principal Investigator should be alerted if the patient is taking any agent known to affect or with the potential for drug interactions. The study team

should check a frequently-updated medical reference for a list of drugs to avoid or minimize use of.

The use of any natural/herbal products or other traditional remedies should be discouraged, but use of these products, as well as use of all vitamins, nutritional supplements, and all other concomitant medications must be recorded in the case report form (CRF) if related to AE or SAE treatment, and other medical conditions deemed necessary by the PI.

Medications that may NOT be administered

No other anti-cancer therapy (chemotherapy, immunotherapy, hormonal therapy (Hormone replacement therapy (HRT) is acceptable), radiotherapy, biological therapy or other novel agent) is to be permitted while the patient is receiving study medication. Live virus and live bacterial vaccines should not be administered while the patient is receiving study medication and during the 30 day follow up period. An increased risk of infection by the administration of live virus and bacterial vaccines has been observed with conventional chemotherapy drugs and the effects with olaparib are unknown.

Restricted concomitant medications

Strong or Moderate CYP3A inhibitors

- Known strong CYP3A inhibitors (e.g., itraconazole, telithromycin, clarithromycin, boosted protease inhibitors, indinavir, saquinavir, nelfinavir, boceprevir, telaprevir) or moderate CYP3A inhibitors (ciprofloxacin, erythromycin, diltiazem, fluconazole, verapamil) should not be taken with olaparib. If there is no suitable alternative concomitant medication then the dose of olaparib should be reduced for the period of concomitant administration. The dose reduction of olaparib should be recorded in the CRF with the reason documented as concomitant CYP3A inhibitor use.
- Strong CYP3A inhibitors – reduce the dose of olaparib to 100mg bd for the duration of concomitant therapy with the strong inhibitor and for 5 half lives afterwards.
- Moderate CYP3A inhibitors - reduce the dose of olaparib to 150mg bd for the duration of concomitant therapy with the moderate inhibitor and for 3 half lives afterwards.
- After the washout of the inhibitor is complete, the olaparib dose can be re-escalated.

Strong or Moderate CYP3A inducers

- Strong (e.g., phenobarbital, phenytoin, rifampicin, rifabutin, rifapentine, carbamazepine, nevirapine, enzalutamide and St John's Wort) and moderate CYP3A inducers (eg. bosentan, efavirenz, modafinil) of CYP3A should not be taken with olaparib.

If the use of any strong or moderate CYP3A inducers are considered necessary for the patient's safety and welfare this could diminish the clinical efficacy of olaparib.

If a patient requires use of a strong or moderate CYP3A inducer or inhibitor then they must be monitored carefully for any change in efficacy of olaparib.

P-gp inhibitors

It is possible that co-administration of P-gp inhibitors (eg amiodarone, azithromycin) may increase exposure to olaparib. Caution should therefore be observed.

Effect of olaparib on other drugs

Based on limited in vitro data, olaparib may increase the exposure to substrates of CYP3A4, P-gp, OATP1B1, OCT1, OCT2, OAT3, MATE1 and MATE2K.

Based on limited in vitro data, olaparib may reduce the exposure to substrates of CYP3A4, CYP1A2, 2B6, 2C9, 2C19 and P-gp. The efficacy of hormonal contraceptives may be reduced if co administered with olaparib. Caution should therefore be observed if substrates of these isoenzymes or transporter proteins are co-administered.

Examples of substrates include:

- CYP3A4 – hormonal contraceptive, simvastatin, cisapride, cyclosporine, ergot alkaloids, fentanyl, pimozide, sirolimus, tacrolimus and quetiapine
- CYP1A2 – duloxetine, melatonin
- CYP2B6 – bupropion, efavirenz
- CYP2C9 – warfarin
- CYP2C19 - lansoprazole, omeprazole, S-mephenytoin
- P-gp - simvastatin, pravastatin, digoxin, dabigatran, colchicine
- OATP1B1 - bosentan, glibenclamide, repaglinide, statins and valsartan
- OCT1, MATE1, MATE2K – metformin
- OCT2 - serum creatinine
- OAT3 -furosemide, methotrexate

Anticoagulant Therapy

Patients who are taking warfarin may participate in this trial; however, it is recommended as standard of care that international normalized ratio (INR) be monitored carefully at least once per week for the first month, then monthly if the INR is stable. Subcutaneous heparin, low molecular weight heparin and novel oral anticoagulants (NOACs) are permitted.

Grapefruit juice

It is not recommended to consume grapefruit juice while on olaparib therapy

6.5 CONCOMITANT THERAPY

Medications or vaccinations specifically prohibited in the exclusion criteria are not allowed during the ongoing trial. If there is a clinical indication for one of these or other medications or vaccinations specifically prohibited during the trial, discontinuation from trial therapy or vaccination may be required. The final decision on any supportive therapy or vaccination rests with the investigator and/or the participants' primary physician.

6.5.1 ACCEPTABLE CONCOMITANT MEDICATIONS

All treatments that the investigator considers necessary for a participant's welfare may be administered at the discretion of the investigator in keeping with the community standards of medical care. Only concomitant medications related to AE or SAE treatment, and other medical conditions deemed necessary by the PI will be recorded on the case report form (CRF). If changes occur during the trial period, documentation of drug dosage, frequency, route, and date may also be included on the CRF.

All concomitant medications received within 28 days before the first dose of trial treatment and 30 days after the last dose of trial treatment should be recorded. If a participant initiates a new anti-cancer therapy within 30 days after the last dose of trial treatment, the 30 day Safety Follow-up visit must occur before the first dose of the new therapy. All concomitant medications administered during SAEs or AESIs are to be recorded. AESIs are defined in Section 8.4.

6.5.1.1 PRIOR MEDICATIONS

The investigator or qualified designee will review prior medication use, including any protocol-specified washout requirement, and record prior medication taken by the participant within 28 days before starting the trial. Treatment for the disease for which the participant has enrolled in this study will be recorded separately and not listed as a prior medication.

6.5.2 RESCUE MEDICINE

Participants should receive appropriate supportive care measures as deemed necessary by the treating investigator. Suggested supportive care measures for the management of AEs associated with study intervention are outlined along with the dose modification guidelines in Appendix 6, Table 10. Where appropriate, these guidelines include the use of oral or IV treatment with corticosteroids, as well as additional anti-inflammatory agents if symptoms do not improve with administration of corticosteroids. Note that several courses of steroid tapering may be necessary as symptoms may worsen when the steroid dose is decreased. For each disorder, attempts should be made to rule out other causes such as metastatic disease or bacterial or viral infection, which might require additional supportive care. The treatment guidelines are intended to be applied when the Investigator determines the events to be related to pembrolizumab or olaparib.

Note: If after the evaluation of the event, it is determined not to be related to pembrolizumab or olaparib, the Investigator does not need to follow the treatment guidance. Refer to Appendix 6, Table 10 for guidelines regarding dose modification and supportive care.

It may be necessary to perform conditional procedures such as bronchoscopy, endoscopy, or skin photography as part of evaluation of the event.

7 STUDY INTERVENTION DISCONTINUATION AND PARTICIPANT DISCONTINUATION/WITHDRAWAL

7.1 DISCONTINUATION OF STUDY INTERVENTION (STOPPING RULES)

The Sponsor-Investigator has the right to terminate this study at any time. Reasons for terminating the study may include, but are not limited to, the following:

- The incidence or severity of adverse events in this or other studies indicates a potential health hazard to patients.
- Patient enrollment is unsatisfactory.
- Quality or quantity of data recording is inaccurate or incomplete
- Poor adherence to protocol and regulatory requirements
- Plans to modify or discontinue the development of the study drug

In the event of Merck or Astrazeneca deciding to no longer supply study drug, ample notification will be provided so that appropriate adjustments to participant treatment can be made.

7.2 PARTICIPANT DISCONTINUATION/WITHDRAWAL FROM STUDY

Participants are free to withdraw from participation in the study at any time upon request.

In addition, the investigator has the right to withdraw a patient from the study at any time should any untoward effect occur. In addition, a participant may be discontinued from study treatment by the investigator or the Sponsor if study treatment is inappropriate, the trial plan is violated, or for administrative and/or other safety reasons. Specific details regarding procedures to be performed at study treatment discontinuation are provided in Section 8.1.4.1.

A participant must be discontinued from study treatment but continue to be monitored in the study and moved to survival follow-up for any of the following reasons:

- The participant or participant's legally acceptable representative requests to discontinue study treatment
- Confirmed radiographic disease progression outlined in Section 8.1.2.6
- Any progression or recurrence of any malignancy, or any occurrence of another malignancy that requires active treatment

Note: Participants with basal cell carcinoma of the skin, squamous cell carcinoma of the skin, or carcinoma in situ (excluding carcinoma in situ of the bladder) who have undergone potentially curative resection do not have to discontinue study intervention.

- Unacceptable adverse experiences as described in Appendix 5 and Appendix 6.
- The participant has a medical condition or personal circumstance which, in the opinion of the treating investigator and/or sponsor, placed the participant at unnecessary risk from continued administration of study treatment.
- Sponsor-Investigator determines it is in the best interest of the patient
- Patient non-compliance with the study treatment or procedure as determined by the treating investigator
- The participant has a confirmed positive serum pregnancy test
- Recurrent Grade 2 pneumonitis
- Discontinuation of treatment may be considered for participants who have attained a confirmed complete response (CR) and have been treated for at least 8 cycles (at least 24 weeks), receiving 2 cycles of the combination including 2 doses of pembrolizumab and at least 80% of the planned doses of olaparib and pembrolizumab beyond the date when the initial CR was declared. These participants may be eligible for second course treatment described in Appendix 7.
- Administrative reasons

Every effort should be made to obtain information on the primary reason for withdrawal from the study or study drug discontinuation, and should be documented in the appropriate eCRF.

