^h Tumor imaging is strongly preferred to be acquired by computed tomography (CT). For the abdomen and pelvis, contrast-enhanced magnetic resonance imaging (MRI) may be used when CT with iodinated contrast is contraindicated, or when local practice mandates it. MRI is the strongly preferred modality for imaging the brain. The same imaging technique regarding modality, ideally the same scanner, and the use of contrast should be used in a participant throughout the study to optimize the reproducibility of the assessment of existing and new tumor burden and improve the accuracy of the assessment of response or progression based on imaging.

ⁱ Evaluation of ECOG at screening is to be performed within 14 days prior to the date of treatment.

^j Medical history will include all active conditions and any condition diagnosed within the prior 10 years that are considered to be clinically significant by the Investigator

^k The investigator or qualified designee will review all new anti-neoplastic therapy initiated after the last dose of trial treatment. If a participant initiates a new anti-cancer therapy within 30 days after the last dose of trial treatment, the 30 day Safety Follow-up visit must occur before the first dose of the new therapy. Once new anti-cancer therapy has been initiated the participant will move into survival follow-up. If the post-trial visit occurs less than 30 days after the last dose of study treatment, a subsequent follow-up phone call should be made at 30 days post the last dose of study treatment to determine if any adverse events have occurred since the post-trial clinic visit

^l ECGs are required within 7 days prior to starting study treatment

^m Laboratory tests for screening or entry into the Second Course Phase should be performed within 10 days prior to the first dose of treatment. After Cycle 1, pre-dose laboratory procedures can be conducted up to 72 hours prior to dosing. Results must be reviewed by the investigator or qualified designee and found to be acceptable prior to each dose of trial treatment.

ⁿ In participants who discontinue study treatment without documented disease progression, every effort should be made to continue monitoring their disease status by tumor imaging using the same imaging schedule used while on study treatment (every 12 weeks \pm 7 days) until the start of a new anticancer treatment, disease progression, pregnancy, death, withdrawal of consent, or the end of the study, whichever occurs first.

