^o Drug diaries will be collected and reviewed at the end of each cycle for Olaparib compliance. Additionally, patients should bring any bottles dispensed for the previous cycle with them to each clinic visit (starting at Day 1 cycle 2) for compliance.

^p The simulation planning scan needs to be completed prior to treatment start date. A radiation oncology assessment will occur at least once during the SBRT course as per standard of care. At 2 weeks post-SBRT, a radiation oncology nurse will call patient to assess for any further toxicities. See section 4.3 for additional radiation details.

^q Only Concomitant Medications related to the treatment of AE or SAE, and other medical conditions deemed necessary by the PI will be recorded.

^r For patients who come off treatment for reasons other than progression, follow up scans will be recorded every 12 weeks. Participants who experience confirmed disease progression or start a new anticancer therapy, will move into the Survival Follow-Up Phase and should be contacted by telephone every 12 weeks to assess for survival status until death, withdrawal of consent, or the end of the trial, whichever occurs first. Patients will be followed for 5 years for survival

^s EOT scans are only required if a scan has not been performed within 8 weeks prior to the EOT visit

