8.1.2.6.2 END OF TREATMENT AND FOLLOW-UP TUMOR IMAGING

In participants who discontinue study treatment, tumor imaging should be performed at the time of treatment discontinuation (\pm 7 days). If previous imaging was obtained within

8 weeks prior to the date of discontinuation, then imaging at treatment discontinuation is not mandatory. In participants who discontinue study treatment due to documented disease progression and the Investigator elects not to implement iRECIST, this is the final required tumor imaging.

In participants who discontinue study treatment without documented disease progression, every effort should be made to continue monitoring their disease status by tumor imaging every 12 weeks to monitor disease status until the start of a new anticancer treatment, disease progression, pregnancy, death, withdrawal of consent, or the end of the study, whichever occurs first.

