8.1.4.3 POST-TREATMENT VISITS

Safety Follow-Up Visit

The mandatory Safety Follow-Up Visit should be conducted approximately 30 days after the last dose of study treatment or before the initiation of a new anti-cancer treatment, whichever comes first. If the post-trial visit occurs less than 30 days after the last dose of study treatment, a subsequent follow-up phone call should be made at 30 days post the last dose of study treatment to determine if any adverse events have occurred since the post-trial clinic visit. All AEs that occur prior to the Safety Follow-Up Visit should be recorded. Participants with an AE of Grade > 1 will be followed until the resolution of the AE to Grade 0-1 or until the beginning of a new anti-cancer therapy, whichever occurs first. SAEs that occur within 90 days of the end of treatment or before initiation of a new anti-cancer treatment will also be followed and recorded. Participants who are eligible for retreatment/crossover with pembrolizumab (as described in Appendix 7) may have up to two safety follow-up visits, one after the Initial Treatment Period and one after the Second Course Treatment.

Follow-Up Visits

Participants who discontinue study treatment for a reason other than disease progression will move into the Follow-Up Phase and should be assessed every 12 weeks (42 ± 7 days) by radiologic imaging to monitor disease status. Every effort should be made to collect information regarding disease status until the start of new anti-cancer therapy, disease progression, death, end of the study or if the participant begins retreatment with pembrolizumab as detailed in Appendix 7. Information regarding post-study anti-cancer treatment will be collected if new treatment is initiated.

Participants who are eligible to receive retreatment with pembrolizumab according to the criteria in Appendix 7 will move from the follow-up phase to the Second Course Phase when they experience disease progression.

Survival Follow up

Participants who experience confirmed disease progression or start a new anticancer therapy, will move into the Survival Follow-Up Phase and should be contacted by telephone every 12 weeks to assess for survival status until death, withdrawal of consent, or the end of the trial, whichever occurs first. Patients will be followed for 5 years for survival.

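### Section 7.2 sends every discontinued participant to telephone survival follow-up, against the sections that keep those who stop without progression on 12-weekly imaging

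*Combined protocol and SAP*

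**What the plan says.** Section 7.2 introduces its list of stop reasons with: "A participant must be discontinued from study treatment but continue to be monitored in the study and moved to survival follow-up". Eleven reasons follow, and only some concern progression.

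Section 8.1.4.3 describes two separate phases. The imaging phase: "Participants who discontinue study treatment for a reason other than disease progression will move into the Follow-Up Phase", with radiologic assessment every 12 weeks. The survival phase: "Participants who experience confirmed disease progression or start a new anticancer therapy, will move into the Survival Follow-Up Phase and should be contacted by telephone". These calls check survival status and recur at 12-week intervals. Footnote r to the Schedule of Events (Section 1.3) repeats this criterion for the survival phase. Section 6.4.1 likewise restricts follow-up to survival once a participant in post-treatment follow-up starts a new therapy.

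Three other places direct imaging after a stop without progression:

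- Footnote r: "For patients who come off treatment for reasons other than progression, follow up scans will be recorded every 12 weeks".
- Section 8.1.2.6.2: "every effort should be made to continue monitoring their disease status by tumor imaging every 12 weeks to monitor disease status".
- Footnote n, in similar best-effort terms, which asks for "monitoring their disease status by tumor imaging using the same imaging schedule used while on study treatment" and then gives the interval as 12 weeks.

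For complete responders who stop, Section 8.1.4.1 prescribes a safety visit and then the Follow-Up Period. Section 8.1.4.3 adds that participants eligible for retreatment "will move from the follow-up phase to the Second Course Phase when they experience disease progression".

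**The concern.** A participant who stops for toxicity without progression cannot be in both phases. Section 7.2 puts that participant in the phase without scans; the other sections put the same participant in the phase with them. Staff are likely to turn to 7.2 when someone stops treatment, so the conflict sits where it can be acted on.

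Two things are at stake. The first is dating progression. Section 9.1 ends PFS at progression or last follow-up and ends duration of response at progression. Section 9.4.3 reports both by Kaplan-Meier, and Section 6.1 schedules PFS looks at 12 and 24 months. Without scans, last follow-up has two readings. If it is the last scan, participants are censored for reasons that may be related to tolerability or outcome. If it is the last telephone call, unscanned time counts as progression-free.

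The second is the second course. Section 7.2 offers it to complete responders in the same item that sends them to survival follow-up, yet Appendix 7 requires radiographic progression after stopping.

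**Working it through.** The plan gives no figure on this point to reproduce. The check is a comparison of text, a count of scheduled scans, and an illustration on assumed inputs.

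**1. The eleven reasons in 7.2 against the other sections.**

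| Reason in 7.2 | Destination elsewhere | Conflict? |
|---|---|---|
| Confirmed radiographic progression | Survival follow-up | No |
| Any progression, or another malignancy needing treatment | Generally survival follow-up, through progression or new therapy | No |
| Positive pregnancy test | Imaging ends under footnote n and 8.1.2.6.2; 8.1.4.3 does not list pregnancy as an end | Partly |
| Participant request | Imaging | Yes |
| Unacceptable adverse events | Imaging | Yes |
| Medical or personal circumstance | Imaging | Yes |
| Sponsor-investigator decision | Imaging | Yes |
| Non-compliance | Imaging | Yes |
| Recurrent Grade 2 pneumonitis | Imaging | Yes |
| Confirmed complete response | Imaging (also 8.1.4.1) | Yes |
| Administrative | Imaging | Yes |

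Outright conflicts: 11 − 3 = 8. This counts list items, not patients. Recurrent Grade 2 pneumonitis is also an Appendix 6 toxicity, so it overlaps with the adverse-event item. The complete-response item is worded as optional despite the mandatory lead-in.

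**2. Scheduled scans lost** by a participant who remains progression-free, if 7.2 is followed literally: floor((horizon − stop week) / 12).

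- Stop at week 13 (an assumed example): (52 − 13)/12 = 3.25, so 3 scans by week 52; (104 − 13)/12 = 7.58, so 7 by week 104.
- Stop in complete response at week 24 (8 cycles × 3 weeks, the minimum treatment in 7.2): (52 − 24)/12 = 2.33, so 2; (104 − 24)/12 = 6.67, so 6.

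**3. Illustration for median PFS.** All inputs are assumptions. Progression is exponential with hazard λ = ln 2, so the median is 1. A share q stops without progression before progressing, with stop hazard g = λq/(1 − q). The hazard after the stop is hλ. Deaths are not counted as events, following the wording of 9.1. The full-imaging median solves the mixture survival = 0.5. Censoring at the stop gives a Kaplan-Meier median of 1. Censoring at the last call gives the t that solves (1 − q)(1 − exp(−(λ + g)t)) = 0.5. Ratios to the full-imaging median:

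| q | Censored at stop (h = 0.5, 1, 2) | Censored at last call (h = 0.5, 1, 2) |
|---|---|---|
| 0.1 | 0.978, 1.000, 1.030 | 1.030, 1.053, 1.084 |
| 0.2 | 0.952, 1.000, 1.064 | 1.078, 1.132, 1.204 |
| 0.3 | 0.919, 1.000, 1.104 | 1.163, 1.265, 1.397 |

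The last-call column lets calls continue past the median for everyone. If calls end at death, with an assumed death hazard after the stop of 0.5 to 2 times λ, simulation brings the 1.397 corner down to about 1.35 to 1.26.

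For scale, if all 26 participants progressed, sampling error alone would span about exp(±1.96/√26) = 0.68 to 1.47 times the median.

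**The case against.** The strongest reply is that the protocol largely handles this elsewhere. Section 7.2 also says participants continue to be monitored, and it points to 8.1.4.1 for discontinuation procedures. The Schedule of Events has a single 12-weekly follow-up column that carries both survival status and tumor imaging, and its footnotes say who is scanned. Nowhere does 7.2 tell a site to stop scanning. All of this is true and makes the harm less likely. It does not cancel the destination that 7.2 names, which is a defined phase without imaging, and 8.1.4.1 itself contradicts 7.2 for complete responders.

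Three stronger readings are tempting, and the documents do not support them.

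- **That all four places make imaging mandatory.** Footnote n and 8.1.2.6.2 ask only for best efforts. Footnote r and the phase assignment in 8.1.4.3 are firmer.
- **That PFS would be biased by as much as 40%.** That figure needs the highest assumed stop rate, a doubled hazard, the last-call reading and calls that outlast death. None of the inputs comes from the documents, and every ratio in the table lies inside the sampling range for 26 participants.
- **That the primary endpoint is compromised.** Section 8.1.2.6.1 separately calls for a confirmatory scan at least 4 weeks after a first response. An effect on response rate is possible if someone stops before response is assessed or confirmed, but it cannot be sized.

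It is also fair to say that Appendix 7 needs radiographic progression, not a scheduled scan, so a clinically prompted scan could serve. What is lost under 7.2 is the scheduled route.

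**Conclusion.** The inconsistency is real and should be corrected. Section 7.2 is the outlier: eight of its eleven reasons send participants to a phase that the rest of the protocol reserves for others, and pregnancy is not handled consistently either.

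The consequence is conditional on a site following 7.2 literally. For someone who stays progression-free it would remove two or three scheduled scans by week 52 and six or seven by week 104 in the examples above. Progression would go undated in PFS and duration of response, and the scheduled route to a second course would be lost for complete responders.

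The effect on the estimates cannot be derived from the documents, and the PFS ratios only illustrate its direction and plausible order. PFS and duration of response are secondary, descriptive and untested. That makes this a worthwhile consistency correction, not a threat to the trial's main conclusion.

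**What to change.** Amend Section 7.2 as follows.

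- **Survival follow-up** applies, once a participant is off all study treatment, at documented progression, at the start of new anticancer therapy, or when imaging ends for another reason such as pregnancy, unless consent is withdrawn. Documented progression means confirmed progression, or first radiologic progression where treatment stops without confirmatory imaging. The second limb is needed for clinically unstable participants (Table 2 and Appendix 4) and for the case in 8.1.2.6.2 that begins "In participants who discontinue study treatment due to documented disease progression and the Investigator elects not to implement iRECIST".
- **All other participants who stop** enter the 12-weekly imaging Follow-Up Phase of 8.1.4.3 until one of the imaging ends in 8.1.2.6.2.
- **Those who qualify under Appendix 7** may enter the second course at progression instead.

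Make three tidying changes in the same amendment, because 7.2 will now rely on these clauses:

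- In 8.1.4.3, correct the gloss on 12 weeks from 42 ± 7 days to 84 ± 7 days (12 × 7 = 84).
- In 8.1.4.3, add pregnancy to the imaging ends.
- In footnote n, delete the reference to the on-treatment schedule, since imaging on treatment is every 9 weeks (8.1.2.6.1), and keep the 12-week interval.

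The cost is a few sentences of amendment text. No scans are added beyond those that 8.1.2.6.2 and 8.1.4.3 already call for.
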